## **II. Methods and Process**

### **1. Participants Recruitment:**

All participants will be recruited from West China Second University Hospital between January, 2018 and December, 2020 based on the inclusion and exclusion criteria of this study. All participants will have signed the informed consent form.

### **2. The Inclusion and Exclusion Criteria**

#### **2.1 For Patients Having EAH**

##### **Inclusion Criteria:**

- (1)  $\leq 40$  years of age;
- (2) Having a strong desire for fertility preservation;

- (3) Histological diagnosis is confirmed as atypical endometrial hyperplasia (EAH) by the designated gynecological pathologists; and
- (4) Having volunteered to participate in this study, signed the informed consent form, and agreed to participate in clinical follow-up.

**Exclusion Criteria:**

- (1) Patients have allergies or contraindications (except for thromboembolic disease, liver dysfunction, hypertension, and diabetes) for the involved drugs;
- (2) Patients have contraindications for pregnancy;
- (3) Patients have serious underlying disease, malignancies at other site(s), acute liver or kidney disease, acute or subacute genital tract infections, and congenital or acquired abnormal uterine development (that may make intrauterine device placement impossible); and
- (4) Patients refuse to participate in clinical follow-up or sign the informed consent form.

**2.2 For subjects with EC**

**Inclusion Criteria:**

- (1)  $\leq 40$  years of age;
- (2) Having a strong desire for fertility preservation;
- (3) Histological diagnosis is confirmed as well-differentiated (grade 1) endometrioid adenocarcinoma by the designated gynecological pathologists, and the progesterone receptors (PgRs) is positive in immunohistochemistry;
- (4) Disease limited to the endometrium (stage 1A) on MRI;
- (5) Serum CA125/199 level is within normal limit (Laparoscopic exploration to rule out ovarian tumor or another metastasis if necessary); and
- (6) Subjects should have undergone counseling to learn fertility-preserving treatment is not standard of care for the treatment of EC, volunteered to

participate in this study, signed the informed consent form, and agreed to participated in clinical follow-up.

**Exclusion Criteria:**

- (1) Patients have allergies or contraindications (except for thromboembolic disease, liver dysfunction, hypertension, and diabetes) for the involved drugs;
- (2) Patients have lynch syndrome (LS);
- (3) Patients have contraindications for pregnancy;
- (4) Patients have serious underlying disease, malignancies at other site(s), acute liver or kidney disease, acute liver or kidney diseases, acute or subacute genital tract infections and congenital or acquired abnormal uterine development (that may make intrauterine device placement impossible); and
- (5) Patients refuse to participate in clinical follow-up or sign the informed consent form.

[figure not shown]
**2.3 Conditions for Withdrawal from the Treatment (meeting any one of the following conditions)**

- (1) The participants volunteer to withdraw from the trial;
- (2) If the participants have PD on the histologic diagnosis; if the participants have PR and NC after 6 to 9 months of progestogen-based therapy; and if the participants have recurrence of disease while preparing for or during pregnancy;
- (3) If the participants cannot tolerate adverse drug reaction and are judged unfit for medical treatment by the clinician-in-charge.

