### **I. Objectives and Introduction:**

In recent years, the number of young patients having atypical endometrial hyperplasia (EAH) and early endometrial cancer (EC) has been gradually increasing. EAH is a precancerous stage of EC, and the risk of developing EC from EAH is the highest (8%~30%). [1, 2] Women who and EC and are younger than 40 years of age account for 2% to 14% of all cases, among whom 70% are nulliparous. [2-5] These women are generally reluctant to undergo a total hysterectomy that would result in loss of fertility; instead, they prefer conservative treatment of EC and EAH.

The conservative treatment for young women with EC and EAH who desire to conceive has remained challenging. Some reports have revealed that oral highly active progestogens are effective as a conservative treatment option. [2] However, traditional treatments as such often have many and severe side-effects and contraindications including thromboembolism and hypertension, and complications including obesity, ovarian dysfunction such as polycystic ovary (PCO) syndrome, and fasting hyperglycemia. [6] These side-effects and contraindications often lead to withdrawal from therapy. Therefore, a new conservative treatment that is largely effective and widely applicable and has relatively mild side effects, is urgent needed.

On the one hand, levonorgestrel-releasing intrauterine system (LNG-IUS) has protects endometria and inhibits its hyperplasia; and on the other hand, it elevates local drug concentration with fewer and milder side-effects and contraindications, more convenient administration, and better effects than oral progestogens in theory. The use of LNG-IUS for the fertility-preserving treatment of EC and EAH has been proposed in many guidelines,[3, 5, 7-12] in which LNG-IUS was suggested as first-line medicine treatment for EAH by RCOG-BSGE. [1] Nevertheless, no appropriately designed randomized controlled trial (RCT) has been identified that investigates the optimal dosage, duration of treatment, lesion regression, and pregnancy rate after therapy in young women with EC and EAH, with regard to the use of LNG-IUS in particular. Therefore, we conducted the current prospective phase II study on fertility-preserving treatment of EC and EAH.

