#### **1. Primary End Points:**

There are two aspects to the primary end points of the study and as follows:

- 1) To value the efficacies of LNG-IUS as fertility-preserving treatment for early EC and EAH by pathologic response. Pathologic response to medicine treatment is categorized as complete response (CR), partial response (PR), no change (NC), and progressive disease (PD). CR is defined as the absence of any hyperplastic or cancerous lesion. PR is defined as the residual lesion with degeneration and atrophy of endometrial glands. NC is defined as residual lesion without degeneration or atrophy of endometrial glands. PD is defined as the appearance of endometrial cancer for EAH and grade 2 (G2) or 3 for EC.
- 2) To compare the rate of pregnancy and alive baby delivery.

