**Comments:**

(1) The basic history collection includes detailed history of prior treatment; with or without contraindications of oral highly active progestogens: hypertension, diabetes (DM), liver function damage, thrombotic disease and so on; with or without reproductive endocrine disease: infertility, PCO syndrome, insulin resistance (IR), impaired fasting glucose (IFG) and so on; with or without any other system disease; surgical history, allergy history; family history especially for carcinomas.

(2) The basic endocrine examinations include sex hormone, anti mullerian hormone (AMH), and insulin release test (IRT) to rule out PCO syndrome, IR, IFG, and DM. Follow-up treatment will be provided when necessary.

(3) If the patients have abnormality in breast ultrasound, she needs to visit the Department of Breast Surgery to evaluate the risk of continuous progesterone treatment.

(4) Based on the inclusion and exclusion criteria of this study, the patients are allocated to one of the arms by central randomization with study site allocation. The arms and interventions and the probability of distribution are as follows:

1) If the patients does not have thromboembolism, liver dysfunction, hypertension, or diabetes, she will be assigned to one of the following two groups, with a probability of 50%, respectively: a) sequential oral medroxyprogesterone acetate (MPA) 500mg QD group; and b) LNG-IUS (Mirena®) group.

2) If the patients are diagnosed of thromboembolism, liver dysfunction, hypertension, or diabetes, she will be assigned to one of the following two groups, with a probability of 50%, respectively: a) intramuscular injection of leuporelin acetate microspheres (GnRH-a) + LNG-IUS group; and b) LNG-IUS (Mirena®) group.

(5) For the groups of oral highly active progestogens, medicine treatment should only be continued if the liver function is normal, which is evaluated by monthly tests.

(6) For the groups of LNG-IUS, the medical device needs to be replaced by a new one on every hysteroscopy to insure adequate drug release

(7) Endometrial tissue sampling for diagnosis should be performed by hysteroscopy every 3 months, and the histologic diagnoses of all specimens are made by two categorized pathologists.

[figure not shown]

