#### **3. Statistics:**

SPSS software will be used for statistical analysis. Survival analysis is used for primary end points and chi-square test for secondary end points.

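### The plan has no analysis set, event or censoring rule for women who stop before complete response; with default censoring at exit, the reported CR rate would exceed the share of randomised women who reach CR

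*Combined protocol and SAP*

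**What the plan says.** - **Outcome.** Section I.1 (Primary End Points) classifies response by histology into complete response, partial response (PR), no change (NC) or progressive disease (PD). "CR is defined as the absence of any hyperplastic or cancerous lesion", so a biopsy is needed. No time point and no not-evaluable category are given.
- **Assessment.** Section II.3.1, comment (7): "Endometrial tissue sampling for diagnosis should be performed by hysteroscopy every 3 months". Section II.3.2, comment (10), is equivalent for EC. Tables 1 and 2 put on-treatment pathology at months 3, 6 and 9. No biopsy is specified for a woman who stops between these visits.
- **Ways off treatment before CR.** Section II.2.3 lists PD and persistent PR/NC, which carry a response category. It also lists "The participants volunteer to withdraw from the trial" and stopping because women "cannot tolerate adverse drug reaction and are judged unfit for medical treatment by the clinician-in-charge", which carry none. Recurrence around pregnancy is listed too, but comes after CR.
- **A further stop for oral progestogen.** Section II.3.1, comment (5), and II.3.2, comment (8), say for the oral groups that "medicine treatment should only be continued if the liver function is normal, which is evaluated by monthly tests". No outcome rule is attached.
- **Analysis.** Section III.3, apart from naming the software, says only: "Survival analysis is used for primary end points and chi-square test for secondary end points".
- **Expected tolerability.** Section I says of traditional oral progestogen treatment: "These side-effects and contraindications often lead to withdrawal from therapy". Section V describes the systemic effects of LNG-IUS as fewer and milder. Neither gives a rate.

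**The concern.** A woman who stops before the month-3 biopsy has no response category. One who stops after a month-3 PR or NC has an interim category, but no rule says whether it is carried forward. The analyst must therefore decide how to count both, possibly after seeing the data.

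The choice matters because the methods answer different questions. Censoring at exit treats a woman who left as if she would have gone on to CR at the same rate as those who stayed. It estimates CR had everyone remained on treatment. Counting her as not CR estimates CR under the treatment as assigned. The plan chooses neither. If stopping differs between arms, the two answers can differ in the size of the treatment effect as well as in the level of CR. With 14 to 30 women per group, reclassifying a few of them can change the result.

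**Working it through.** The plan states no CR rate, withdrawal rate or censoring rule for this analysis, so there is no figure of its own to reproduce. All rates below are assumptions, except the 69% and 90% in step 2. Those are the pooled EAH regression rates for oral progestogen and LNG-IUS quoted in section V as background; they are not stated as the design basis.

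**Step 1. One arm.** Assume the chance of CR among women still on treatment is h1 = 0.35, h2 = 0.45 and h3 = 0.45 at months 3, 6 and 9. Assume a fraction w of women without CR leaves before each of the month-3 and month-6 biopsies.

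- Censored at exit: 1 − KM = 1 − (1 − h1)(1 − h2)(1 − h3) = 1 − 0.65 × 0.55 × 0.55 = 0.803, whatever w is.
- Share of randomised women with CR: (1 − w)h1 + (1 − w)²(1 − h1)h2 + (1 − w)²(1 − h1)(1 − h2)h3.
- Total leaving: w + w(1 − w)(1 − h1).

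For w = 0.05: 0.3325 + 0.2640 + 0.1452 = 0.742, with 0.05 + 0.0309 = 8.1% leaving.

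| w | Total leaving | 1 − KM | CR among randomised | Gap (points) | SE of that CR rate at n = 20 |
|---|---|---|---|---|---|
| 0.05 | 8% | 80.3% | 74.2% | 6 | 9.8 |
| 0.10 | 16% | 80.3% | 68.2% | 12 | 10.4 |
| 0.15 | 23% | 80.3% | 62.5% | 18 | 10.8 |
| 0.20 | 30% | 80.3% | 57.0% | 23 | 11.1 |

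SE = √(p(1 − p)/20), with p the CR share among randomised women. The gap runs from about 0.6 to 2.1 SE.

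**Step 2. Two arms, both directions.** Take CR if all stayed as 69% for MPA and 90% for LNG-IUS, with a constant chance h at each biopsy: h = 1 − (1 − p)^(1/3), which is 0.323 for MPA and 0.536 for LNG-IUS. Let w apply before all three biopsies. CR among randomised women is the sum over k = 1, 2, 3 of (1 − w)^k (1 − h)^(k−1) h. Censoring shows 90 − 69 = 21 points in every row.

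| MPA leaving | LNG-IUS leaving | CR among randomised, MPA vs LNG-IUS | Difference (points) | Shown with censoring |
|---|---|---|---|---|
| 10% | 8% | 63% vs 83% | 20 | 21 |
| 20% | 8% | 58% vs 83% | 26 | 21 |
| 37% | 8% | 47% vs 83% | 36 | 21 |
| 10% | 16% | 63% vs 77% | 14 | 21 |
| 10% | 30% | 63% vs 65% | 2 | 21 |

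Censoring understates the LNG-IUS advantage when MPA stopping is clearly higher, and overstates it when LNG-IUS stopping is higher.

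**Step 3. Where the MPA comparison applies.** From section III.1, planned numbers are 3 × 18 = 54 (EC without contraindications), 2 × 30 = 60 (EC with), 2 × 20 = 40 (EAH without) and 2 × 14 = 28 (EAH with), in all 182. The two strata with contraindications, 60 + 28 = 88 women, compare GnRH-a + LNG-IUS with LNG-IUS and have no MPA arm.

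**The case against.** **Censoring is not stated.** Keeping stoppers at risk as not CR, or treating exit as a competing event, is also survival analysis and fits section III.3 equally well. This stands: the defect is a missing rule, and the figures above show what follows if the usual default fills it. Censored women are also not simply dropped. They count at risk until they leave; only those leaving before month 3 contribute nothing to the CR estimate.

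**On-treatment CR is a legitimate target.** Section I.1 speaks of response to medicine treatment, and side effects are compared separately. This stands too: overstatement here is relative to CR among all randomised women. The plan still has to say which quantity it wants.

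**Unequal stopping is less certain than it looks.** Section I blames side effects and contraindications together, and section V ties withdrawal to complications such as obesity, hypertension and impaired glucose metabolism. Women with thromboembolism, liver dysfunction, hypertension or diabetes are routed to strata without MPA, which removes part of the cause. What remains is the tolerability rationale for LNG-IUS and the liver-function stop worded for the oral groups only.

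**A stronger inference is tempting:** that the planned analysis hides any LNG-IUS advantage. The documents do not support it. MPA is absent for 88 of 182 women, one of the three arms in EC without contraindications combines MPA with LNG-IUS, and the bias reverses if LNG-IUS has more stopping. Simulated trials of 20 per group, with the step 1 CR chances equal in both arms, can look striking: with about 23% or 30% leaving MPA and 3% leaving LNG-IUS, a censored log-rank test rejects in about 5%, against about 16% or 25% when leavers stay in as not CR. But equal on-treatment CR makes 5% simply the test holding its level. With 8% against 3% leaving, or 16% against 8%, the figures are about 5% against 6%.

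**Conclusion.** The concern holds as a gap in specification. The plan names survival analysis for its primary end points, allows exits before CR, and says nowhere who is analysed or how those women are counted. With censoring at exit, reported CR exceeds the all-randomised share by 6 points at 8% withdrawal and by 23 points at 30%, under the CR chances assumed in step 1.

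The effect on the comparison is conditional. Against MPA, an LNG-IUS advantage may be understated if MPA is worse tolerated, and would be exaggerated if LNG-IUS has more stopping. For GnRH-a + LNG-IUS versus LNG-IUS the documents support no direction. Because no withdrawal rates are given, the size is a range and not an estimate. The plan should be changed, since the fix works whichever arm is worse tolerated.

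**What to change.** In section III.3:

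1. Define the primary response as CR by month 9 in all randomised women, analysed in the group assigned.
2. Score a woman who leaves treatment before a documented CR, for any reason (choice, intolerance, liver-function stop, PD, persistent PR/NC), as not CR and keep her in the denominator. PD and persistent PR/NC need the rule as well, because censoring them would also inflate CR.
3. In any time-to-CR display, keep her at risk to month 9 or treat exit as a competing event. Do not censor her at exit.
4. Report the analysis restricted to women with a post-treatment biopsy as a sensitivity analysis, with counts of withdrawals by reason and arm.

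This is SAP wording only, with no added visits or patients. The cost is in interpretation: the CR rate then mixes efficacy with tolerability and will be lower to the extent that women stop early. Show the on-treatment rate beside it.

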**3. Study Design**

**3.1 For Patients Having EAH**

The treatment schedule for EAH is summarized in Figure 1 and Table 1.

**Fig. 1** Study design. EAH, atypical endometrial hyperplasia; EC, endometrial cancer; MPA, medroxyprogesterone acetate; QD, once a day; LNG-IUS, Levonorgestrel-Releasing intrauterine system, Mirena®, Bayer Health Care Pharmaceutical Inc., Wayne, NY; GnRH-a, gonadotropin-releasing hormone agonists, Leuporelin acetate microspheres; mo, months; CR, complete response; PR, partial response; NC, no change; PD, progressive disease

**Table 1** The treatment schedule for atypical endometrial hyperplasia

Visits	1st	2nd	3rd	4th	5th	6th	7th	8th	9th	10th	11th	12th
Times	-1	-1/4	0	1	2	3	4	5	6	7	8	9

(month)												
Procedures	Pre-screening	Screening	Treatment Beginning	The 1st cycle			The 2nd cycle			The 3rd cycle (if necessary)		
History collection	√					√			√			√
Physical examination	√	√	√			√			√			√
Weight	√		√	√	√	√	√	√	√	√	√	√
Thinprep cytology test (TCT)	√											
Breast ultrasound	√											
Gynecological ultrasound	√					√			√			√
Endocrine examinations	√											
Liver function test	√			√	√	√	√	√	√	√	√	√
Coagulation function test	√					√			√			√
Pathology examinations	√	√				√			√			√
Hysteroscopy		√				√			√			√
Criteria	√	√				√			√			
Informed consent			√									
Random assignment			√									
Medical treatment			√	√	√	√	√	√	√	√	√	
Response evaluation						√			√			√
Adverse resection				√	√	√	√	√	√	√	√	√
Adverse events			√	√	√	√	√	√	√	√	√	√

**Comments:**

(1) The basic history collection includes detailed history of prior treatment; with or without contraindications of oral highly active progestogens: hypertension, diabetes (DM), liver function damage, thrombotic disease and so on; with or without reproductive endocrine disease: infertility, PCO syndrome, insulin resistance (IR), impaired fasting glucose (IFG) and so on; with or without any other system disease; surgical history, allergy history; family history especially for carcinomas.

(2) The basic endocrine examinations include sex hormone, anti mullerian hormone (AMH), and insulin release test (IRT) to rule out PCO syndrome, IR, IFG, and DM. Follow-up treatment will be provided when necessary.

(3) If the patients have abnormality in breast ultrasound, she needs to visit the Department of Breast Surgery to evaluate the risk of continuous progesterone treatment.

(4) Based on the inclusion and exclusion criteria of this study, the patients are allocated to one of the arms by central randomization with study site allocation. The arms and interventions and the probability of distribution are as follows:

1) If the patients does not have thromboembolism, liver dysfunction, hypertension, or diabetes, she will be assigned to one of the following two groups, with a probability of 50%, respectively: a) sequential oral medroxyprogesterone acetate (MPA) 500mg QD group; and b) LNG-IUS (Mirena®) group.

2) If the patients are diagnosed of thromboembolism, liver dysfunction, hypertension, or diabetes, she will be assigned to one of the following two groups, with a probability of 50%, respectively: a) intramuscular injection of leuporelin acetate microspheres (GnRH-a) + LNG-IUS group; and b) LNG-IUS (Mirena®) group.

(5) For the groups of oral highly active progestogens, medicine treatment should only be continued if the liver function is normal, which is evaluated by monthly tests.

(6) For the groups of LNG-IUS, the medical device needs to be replaced by a new one on every hysteroscopy to insure adequate drug release

(7) Endometrial tissue sampling for diagnosis should be performed by hysteroscopy every 3 months, and the histologic diagnoses of all specimens are made by two categorized pathologists.

[figure not shown]
(8) After 6 months' continuous progestogen-based therapy, if the patients has PR/NC, progestogen-based therapy should be continued for one more cycle (3 months), and if the patient still has PR/NC, she will withdraw from this trial and undergo hysterectomy; if the patients has CR at the second or third endometrial evaluation, fertility treatment will be initiated immediately; and if the patients has documented progression on the biopsies at any time, the protocol treatment will be stopped and hysterectomy be recommended.

(9) The option of natural conception or assisted reproduction should be discussed with the fertility specialist in the reproduction center of our hospital; assisted reproduction is recommended if the patients 1) has history of infertility; 2) has risk factors for infertility such as PCO syndrome, obesity, diabetes, and lack of ovulation; or 3) suffers from failed pregnancies after 6 months of natural conception.

- (10) If the patient succeeds in conceiving, she will receive professional prenatal examinations from the obstetrics specialist in our hospital.
- (11) All the professors in the Department of Obstetrics and Reproductive Center of our hospital are on this research team.
- (12) Long-term follow-up will proceed even after treatments are finished, and corresponding clinical treatments will be provided for patients with different conditions.

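### Prior hormonal treatment of the lesion is neither limited at entry nor used in stratification or analysis, so the primary response mixes untreated and pre-treated disease

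*Combined protocol and SAP*

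**What the plan says.** **Entry.** For EAH the disease criterion is histological: "Histological diagnosis is confirmed as atypical endometrial hyperplasia (EAH) by the designated gynecological pathologists" (Section II.2.1). For EC it is "Histological diagnosis is confirmed as well-differentiated (grade 1) endometrioid adenocarcinoma by the designated gynecological pathologists", with positive progesterone receptors, MRI stage and tumour markers added (Section II.2.2). The only exclusion that concerns the study drugs is "Patients have allergies or contraindications (except for thromboembolic disease, liver dysfunction, hypertension, and diabetes) for the involved drugs", and it appears in both lists. Neither list mentions earlier or ongoing progestogen, LNG-IUS or GnRH-a, a washout, or earlier non-response.

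**Baseline record.** Sections II.3.1 and II.3.2, Comments (1), both state: "The basic history collection includes detailed history of prior treatment". No use of this information is described.

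**Failure rule.** Section II.2.3 ends treatment "if the participants have PR and NC after 6 to 9 months of progestogen-based therapy". Section II.3.1 Comments (8) and Section II.3.2 Comments (11) give the working version: residual disease at 6 months leads to one further 3-month cycle, and residual disease after that leads to leaving the trial.

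**Stratification and analysis.** Section III.1 stratifies on contraindication to oral progestogen. Section III.3 names survival analysis for the primary end points and the chi-square test for the secondary ones, with no covariate, subgroup or sensitivity analysis.

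**The concern.** Pathologic response is a primary end point (Section I.1). A woman whose lesion has persisted through months of progestogen, a woman part-way through a course with a regressing lesion, and an untreated woman plausibly differ in their chance of CR and in how soon it comes, whichever arm they join. The plan asks for the information that separates them and then leaves it unused.

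Three things are at stake:

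- **Interpretation.** CR rates from an undescribed mixture answer neither the first-line nor the second-line question.
- **Sensitivity.** If pre-treated women respond alike in all arms, they shrink the difference the trial can see.
- **Balance.** In groups of 14 to 30, a prognostic factor that is neither stratified nor adjusted for can be visibly uneven by chance.

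The documents also do not fit together. Residual disease after 6 to 9 months ends treatment for a participant, while a woman who reached that state elsewhere meets the written entry criteria and can be assigned to the same drug class.

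**Working it through.** **Step 1: does any criterion screen out pre-treatment?** The four written lists were read item by item. Age, fertility wish, histology, consent, drug allergy or contraindication, pregnancy contraindication and other disease do not depend on earlier treatment. For EC, receptor positivity describes the tumour and not past exposure, and the Lynch syndrome exclusion is unrelated. A woman with residual EAH after 9 months of progestogen elsewhere therefore passes.

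**Step 2: chance imbalance.** Group sizes come from Section III.1: 14 (EAH with contraindications), 20 (EAH without), 18 (EC without, three groups) and 30 (EC with). The pre-treated share f is not in the documents; 5% to 30% is assumed. With X1 and X2 independent Binomial(n, f), the quantity is P(|X1 − X2| ≥ 0.20n), for any two given arms. The smallest whole number of women reaching 20 points is 3, 4, 4 and 6 at n = 14, 18, 20 and 30.

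| f (assumed) | n=14 | n=18 | n=20 | n=30 |
|---|---|---|---|---|
| 5% | 3% | 1% | 1% | 0.2% |
| 10% | 11% | 5% | 6% | 2% |
| 20% | 23% | 14% | 16% | 7.5% |
| 30% | 30% | 20% | 23% | 12% |

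**Step 3: what a 20-point gap does to CR.** Contribution to the arm difference = gap × (CR untreated − CR pre-treated).

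- All pre-treated women resistant, CR 80% against 40% (assumed): 0.20 × 40 = 8 points. With f = 30%, overall CR is 0.7 × 80% + 0.3 × 40% = 68%.
- Half resistant at 40% and half no different from untreated at 80%: pre-treated CR is 60%, and the contribution is 0.20 × 20 = 4 points.
- If carry-over lifts the second half above 80%, the contribution falls below 4 points, and it can reverse if carry-over dominates.

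For scale, the standard error of an arm difference at 68% CR is √(2 × 0.68 × 0.32 / n): 17.6, 15.5, 14.8 and 12.0 points at n = 14, 18, 20 and 30. Eight points is 0.45 to 0.66 of one standard error.

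**Step 4: dilution.** The plan states no response rates, so its sample sizes cannot be reproduced and a design effect has to be assumed. With 20 per group, two-sided alpha 0.05 and one arm at 90%, 80% power needs the other arm at about 50.7%, a difference of 39.3 points. If a share f has the same CR (0% to 40%) in both arms, the difference becomes (1 − f) × 39.3.

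| f (assumed) | Difference (points) | Power, 20 per group | n per group for 80% power |
|---|---|---|---|
| 0% | 39.3 | 80% | 20 |
| 10% | 35.4 | 65–68% | 27–28 |
| 20% | 31.4 | 52–55% | 36–38 |
| 30% | 27.5 | 41–43% | 49–51 |

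This is the unfavourable case, in which every pre-treated woman is resistant and gains nothing from one arm over the other.

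**The case against.** **Randomisation already protects the comparison.** This stands. A reader might infer that the arms are systematically biased. They are not, because prior treatment is balanced on average and chance imbalance is within the test's error rate. What remains is dilution, avoidable noise and unclear interpretation.

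**Pre-treated women may be few.** The documents give no share. At 5% to 10% the imbalance probabilities are small, 11% at most. The point rests on the missing provision and not on a known frequency.

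**The direction is not fixed.** Resistant women lower CR and carry-over raises it. A reader might take the fall from 80% to 68%, or the 8-point difference, as expected effects. They are one end of a range.

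**Pre-trial months might count towards the 6-to-9-month rule.** A reader might infer this because Section II.2.3 names no starting point. Tables 1 and 2 largely answer it: treatment start and random assignment share month 0, and the three cycles are numbered from there.

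**Broad entry may be intended.** Section V speaks of women unable to tolerate highly active progestogens, some of whom will have taken them, and Section I does not confine the objective to first-line use. An exclusion would also cost recruits at a single centre with a three-year window. This is a fair reason not to insist on exclusion. It is no reason to leave the factor out of the analysis.

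**Conclusion.** The point holds in this form: the plan admits pre-treated women without limit, collects their treatment history, and uses it in neither stratification nor analysis. The result is a primary response that is hard to interpret and possibly diluted, with a real but assumption-dependent chance of uneven arms. A gap of 20 points or more has probability 3% to 30% at 14 per group and 0.2% to 12% at 30 per group, as the pre-treated share runs from 5% to 30%. The power losses depend on further assumptions about the design difference and about resistant women.

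The documents do not support a claim of systematic bias, of a known number of treatment failures being enrolled, or of a predictable shift in CR. Figures 1 and 2 could not be read in the copy examined. If either carries an entry restriction, the written criteria should be brought into line with it.

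**What to change.** 1. Code prior hormonal treatment of the current lesion (yes/no) from the history already taken, before randomisation.
2. In Section III.3, include it as a covariate or stratum in the primary response analysis, read here as time to CR since survival analysis is named.
3. Report it by arm in each of the four disease-by-contraindication strata.
4. Show response in previously untreated women as a supporting analysis.
5. Reconcile the entry criteria (Sections II.2.1 and II.2.2) with the failure rule (Section II.2.3; Section II.3.1 Comments (8); Section II.3.2 Comments (11)), and state whether pre-treated women are eligible. Whether to exclude them is for the clinical team.

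The cost is one coded variable and a few lines of analysis text. There is a slight loss of precision from adjustment in small strata if few women are pre-treated. Adjustment deals with imbalance but does not undo dilution. The untreated-only analysis addresses that on fewer women: at 20 per group and an assumed 30% share, about 0.7 × 20 = 14 per group. It should therefore be presented as supporting.
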